9.3 VARIABLES

9.3.1 Exposure

Person-time observed from index date to the date of outcome or censoring event will be determined for both the NOCDURNA group and the LUTS group.

Person-time exposed will start accumulating from the index date. For the NOCDURNA group this will be the date that the first-ever prescription for NOCDURNA was dispensed. Thus, this study will include patients who are new users of NOCDURNA. For the LUTS group, this will be the date of a first-ever prescription of a drug with the ATC code G04BD or G04C within the study time period. Thus, the LUTS groups will include patients who are new users of treatments for lower urinary tract symptoms.

Specific episode of exposure to NOCDURNA will be established using information on dispensed prescriptions for NOCDURNA. Information will include drug and substance name, ATC code, formulation, strength and dispensed amount of drug, as available in each data source.

On-treatment person-time will be constructed from single prescriptions or multiple sequential prescriptions for NOCDURNA and the drugs defining the LUTS cohort. The duration of individual prescriptions for NOCDURNA will be calculated based on the days supplied, as estimated from the number of oral lyophilisates dispensed and the recommended daily dosage, one oral lyophilisate per day. The estimated end date of a prescription will be the date it was dispensed plus the days supplied. Sequentially dispensed prescriptions for NOCDURNA will be bridged into continuous on-treatment episodes if each subsequent date the drug was dispensed was within the days supplied by the preceding prescription plus a period equivalent to the days supplied multiplied by 2 (*i.e.*, the permissible gap). In case of prescription overlaps, the number of overlapping days will be added to the estimated end date of the subsequent prescription. The first treatment period will end when there is no subsequent prescription dispensed within the days supplied from the preceding prescription plus the defined permissible gap. Prescriptions of LUTS-defining drugs (ATC code G04BD or G04C) will be treated analogous to NOCDURNA in terms of permissible gap. Treatment restarts following treatment holiday will not be evaluated in this study.

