In addition, a subgroup analysis of all patients adhering to the label as assessed by the proxy based on diagnosis and contra-indications (as available) will be conducted.

7. MACE and VTE events resulting in treatment withdrawal of NOCDURNA

Serious events resulting in treatment withdrawal of NOCDURNA will be evaluated in the NOCDURNA exposed group only. Treatment cessation of NOCDURNA, defined by a time after prescription longer than the permissible gap (see section 9.3.1), will be defined as the end of an on-treatment period. Serious events will be evaluated in 14 days prior to the treatment cessation date.

Serious MACE and VTE events will be defined as a primary or secondary diagnosis of MACE or VTE recorded in a hospital intensive care unit. This can be only evaluated in Sweden.

Variable	Definition	Countries in which outcome assessed		
Primary outcome				
Symptomatic hyponatraemia	Primary or secondary diagnosis of hyponatraemia (E87.1)	 Denmark Germany (hospital discharge diagnosis) Sweden 		
Secondary outcomes				

Table 2: Definitions of primary and secondary outcome variables

Post Authorization Safety Study (PASS) Protocol Study Number: 000248

Variable	Definition	Countries in which outcome assessed
Hyponatraemia requiring hospital intensive care	Primary or secondary diagnosis of hyponatraemia (E87.1) from hospital intensive care	Sweden
Clinically significant hyponatraemia including hyponatraemia by severity	Serum sodium concentration <130 mmol/L Mild hyponatraemia: serum sodium concentration 130-<135 mmol/L Moderate hyponatraemia: serum sodium concentration >125-<130 mmol/L Severe hyponatraemia: serum	• Denmark
All-cause mortality	sodium concentration ≤125 mmol/L Death from any cause	DenmarkSwedenGermany
Major cardiovascular events	Primary or secondary diagnosis of cardiovascular death (underlying or contributory cause), myocardial infarction or stroke	 Denmark Germany (non-fatal events only; discharge diagnosis) Sweden
Major venous thromboembolic events	Primary or secondary diagnosis of deep vein thrombosis, pulmonary embolism, portal vein thrombosis, or death from either of these conditions as the underlying or contributory cause	 Denmark Germany (non-fatal events only; discharge diagnosis) Sweden

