9.7.2.9 Secondary objective 7: Comparative analyses

Where possible, for the comparative analyses of primary and secondary outcomes of interest, the same analyses (Poisson regression) as in Section 9.7.2.1 will be applied but now with treatment group (NOCDURNA/LUTS) as an additional factor. To investigate if the incidence rate ratio (IRR) for the Poisson regression of NOCDURNA to LUTS depend on confounders, treatment by confounder interaction terms will be investigated to see if and to what extent (quantitative or qualitative) the IRR depend on the respective confounding factor. These multiple regression methods will be detailed in the SAP.

9.7.2.10 Secondary objective 8: Cardiovascular and thromboembolic events of interest resulting in treatment withdrawal

The analysis of this outcome will be performed analogous to that of incident events of symptomatic hyponatraemia (see 9.7.2.1) for NOCDURNA only. MACE and VTE events considered to be associated with treatment cessation will be those events for which the event date occurs within 14 days prior to the treatment cessation date (see section 9.3.1). Serious MACE and VTE events will be defined as a primary or secondary diagnosis of MACE or VTE recorded in a hospital intensive care unit. This can be only evaluated in Sweden.

9.7.2.11 Secondary objective 9: Incidence rate in patients stratified according to the label by proxy

The analysis of this outcome will be performed analogous to that of incident events of symptomatic hyponatraemia (see 9.7.2.1) for NOCDURNA only. The subgroup of patients adhering to the label will be defined by a proxy based on diagnosis and contra-indications as available in the respective registries. This will be detailed in the statistical analysis plan

In this analysis the outcomes specified as the primary objective and secondary objectives 1-6 will be repeated for the NOCDURNA only patients. The subgroup of patients adhering to the label will be defined by a proxy based on diagnosis and contra-indications as available in the respective registries based on the information in the SmPC. Two population will be created for all NOCDURNA patients, one with contra-indication for treatment and another as the remaining NOCDURNA patients without contra-indication. The contra-indication for treatment must be present before the first recorded dispensation of NOCDURNA. This approach will be detailed in the statistical analysis plan

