9 EXPOSURE AND TREATMENT COMPLIANCE

9.1.1 Extent of Exposure

Exposure person-time will be defined for Nocdurna ® patients from the date of first Nocdurna ® prescription. For comparative analyses, equivalent person-time in the LUTS contextual cohort group will be defined from the index date.

Person-time observed from index date to the date of outcome or censoring event will be determined for both the Nocdurna ® group and the LUTS group.

Estimation of exposure periods: Duration of exposure to the respective study drug (Nocdurna \mathbb{R} or LUTS treatment) will be defined based on the estimated supply of drug dispensations. To estimate the supply, the total drug amount of a dispensation is converted into defined daily doses (DDDs; sex-specific DDD for Nocdurna: 25 µg for females, 50 µg for males). The days supplied added to the dispensation date will approximate the end date of a dispensation.

Overlapping dispensations: If a new dispensation of the respective study drug occurs prior to the end date of the previous dispensation, the estimated end date of the latest dispensation will be postponed by the days of overlap.

Permissible gap: If there is a gap after the estimated end date of a dispensation (i.e. there is no new dispensation of the respective study drug covering the first day after the end date of the latest dispensation), the exposure period will be extended. A period equal to the days supplied by the latest dispensation (DDD*1) will be added to the end date of the latest dispensation. In other words, the exposure period continues if a subsequent dispensation occurs within the timeframe of the permissible gap.

End of exposure period: If no subsequent dispensation occurs within the timeframe of a permissible gap, the end of the exposure period will be the last day of the permissible gap.

The above-mentioned considerations apply to both Nocdurna ® and drugs for the treatment of LUTS. For both the Nocdurna ® and LUTS groups, exposure periods start at cohort entry.

There are multiple preparations (multiple ATC codes) defining the treatment of LUTS. All those preparations are considered when defining exposure to LUTS treatment, i.e. concomitant use and switching between different preparations to treat LUTS are allowed within a patient's exposure period. In the Nocdurna ® group, however, only Nocdurna ® dispensations are considered to define exposure periods.

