The analysis will first calculate the treatment cessation date and then within a 14 days window before the treatment cessation date examine if there is a MACE or VTE event reported from the intensive care register.

Secondary objective 9: Incidence rate in patients stratified according to the label by proxy

The analysis of this outcome will be performed analogous to that of incident events of symptomatic hyponatraemia but only for the Nocdurna ® patients. The subgroup of patients adhering to the label will be defined by a proxy based on diagnosis and contra-indications as stated in the SmPC and the data for classifying the patients according to contraindications should be done as available in the respective registries.

Two population will be created for all Nocdurna ® patients, one with contra-indication for treatment and another as the remaining Nocdurna ® patients without contra-indication. The contra-indication for treatment must be present before the first recorded dispensation of Nocdurna ®.

The following diseases will be considered as contraindications for the prescription of Nocdurna ®, if the diseases are found before or at the index date.

- History of hyponatraemia
- Polydipsia
- Congestive heart failure (chronic)
- Kidney disease (chronic kidney disease stage 3 and over)
- Syndrome of inappropriate antidiuretic hormone secretion (SIADH)

The ICD 10 codes for the above can be found in the given in Table 71. The analysis will be done by using the SAS macro 'Nocdurna_mac' and changing the macro call with 'compare=Off label' and creating a class group with 'Off label' instead of 'LUTS' as described in section 16.1

The analysis of the sub-population will be done for the primary objective and for secondary objective 2, 3, 4, 5a, 5b and 6.

Observe that this analysis is changed from the description in the study protocol.

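### The 14-day look-back for events that led to NOCDURNA withdrawal is tied to a cessation date well after supply has ended, so it misses most of the events it targets

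*Protocol*

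**What the plan says.** Outcome 7 in Protocol 9.3.2.2 concerns MACE and VTE leading to withdrawal of NOCDURNA. It is restricted to NOCDURNA patients and to events recorded in intensive care, so only Sweden can contribute. Cessation is "defined by a time after prescription longer than the permissible gap (see section 9.3.1), will be defined as the end of an on-treatment period", and "Serious events will be evaluated in 14 days prior to the treatment cessation date". Protocol 9.7.2.10 repeats the rule for the analysis: the "event date occurs within 14 days prior to the treatment cessation date".

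Protocol 9.3.1 builds the on-treatment period. Days supplied equal the number of lyophilisates at one per day. Dispensings are bridged if the next falls within the days supplied "plus a period equivalent to the days supplied multiplied by 2". The first period ends when there is "no subsequent prescription dispensed within the days supplied from the preceding prescription plus the defined permissible gap".

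The SAP keeps the look-back. Section 10.2.9 says: "The analysis will first calculate the treatment cessation date and then within a 14 days window before the treatment cessation date examine" the intensive-care register. SAP 9.1.1, however, sets the gap at one times the days supplied, and without a refill "the end of the exposure period will be the last day of the permissible gap".

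Two other passages point elsewhere. Protocol 9.2.3.1 speaks of end of treatment plus 7 days and refers back to 9.3.1. A sentence late in SAP 9.1.1 puts end of treatment, once the last dispensed drug is used up, at the last day covered at the standard dose.

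**The concern.** The registers hold dispensing dates, not stop dates; Protocol 9.9.2 says discontinuation is not recorded. A patient who stops because of an infarction, stroke or thrombosis was still taking the drug when the event occurred, so the event falls while the last supply lasts. The computed cessation date comes only after that supply and the whole permissible gap have passed. A 14-day look-back from that date searches a period when, by the study's own assumptions, the patient has no drug left.

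The analysis would then miss the events it is meant to find and count others that cannot have prompted a stop. This is a stated secondary objective of a safety study required by regulators, and intensive-care events in one country will be few. A rate near zero produced by the position of the window could be taken as evidence of safety.

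**Working it through.** The plan gives no event count or expected rate for this outcome, so there is no figure to reproduce. The check is timeline arithmetic.

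**Inputs from the documents**
- Look-back: 14 days (Protocol 9.3.2.2 and 9.7.2.10; SAP 10.2.9).
- Gap: 2 x S (Protocol 9.3.1) or 1 x S (SAP 9.1.1).
- Intake: one lyophilisate per day (Protocol 9.3.1), all consumed (Protocol 9.9.2).
- Slower use: 50% adherence, used for sizing in Protocol 9.5.3. SAP 10.1.3 also codes as-needed instructions as 0.5 per day.

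**Assumptions**
- S is 30 or 90 days. The Protocol gives no pack size; 90 days appears only in the illustrative schematic in SAP 9.1.1.
- Stop-causing events are uniformly distributed over the time the last supply lasts.

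**Formulas.** Day 0 is the last dispensing. With gap multiple m, cessation is at S(1+m) and the window runs from S(1+m)-14 to S(1+m). With intake of a tablets per day, stop-causing events fall on days 0 to S/a. The share captured is the overlap of the two intervals divided by S/a.

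| Cessation read as | S | Window (days) | Captured, 1 per day | Captured, 0.5 per day |
|---|---|---|---|---|
| Supply + 2S (Protocol 9.3.1) | 30 | 76-90 | 0% | 0% |
| Supply + 2S (Protocol 9.3.1) | 90 | 256-270 | 0% | 0% |
| Supply + 1S (SAP 9.1.1) | 30 | 46-60 | 0% | 14/60 = 23% |
| Supply + 1S (SAP 9.1.1) | 90 | 166-180 | 0% | 14/180 = 8% |
| End of supply | 30 | 16-30 | 14/30 = 47% | 14/60 = 23% |
| End of supply | 90 | 76-90 | 14/90 = 16% | 14/180 = 8% |

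**Where the result turns**
- Protocol gap, one per day: the window lies wholly after supply when 3S-14 > S, that is S > 7. It opens 76-30 = 46 days after the last tablet for S=30 and 256-90 = 166 days after for S=90.
- Protocol gap, 0.5 per day: tablets last to day 2S, and 3S-14 is at or beyond 2S when S is 14 or more, so capture stays at 0%.
- Any capture under the Protocol gap needs adherence below S/(3S-14): 30/76 = 39% for S=30 and 90/256 = 35% for S=90.
- SAP gap, one per day: 2S-14 is at or beyond S when S is 14 or more, so capture is 0%.
- End of supply, one per day: capture is 14/S, below one half for any S above 28.

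Carry-over from overlapping dispensings moves the end of supply and the cessation date by the same number of days, so it does not change these conditions.

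**The case against.** The strongest reply is that the cessation date is not fixed. Protocol 9.3.1 can be read as using the gap to test whether treatment stopped, not to date the stop. The 7-day addition in Protocol 9.2.3.1 would be odd if two further supply lengths were already included, and the late sentence in SAP 9.1.1 puts end of treatment at end of supply. On that reading 47% or 16% is captured. Slower use also produces some capture under the SAP gap, and supplies of about two weeks or less behave better on the SAP and end-of-supply readings. This part stands: a reader might infer that no stop-causing event can ever be counted, and the documents do not support that, because neither pack size nor actual intake is given and the wording conflicts. The end-of-supply reading is still not the natural one here, since outcome 7 itself ties cessation to "defined by a time after prescription longer than the permissible gap".

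A reader might also infer that MACE and VTE are lost to the study. They are not: both are counted from the index date under objectives 5a and 5b, and intensive-care MACE and VTE are reported for Sweden. Only their attribution to withdrawal is affected; the primary objective and the comparisons with LUTS are untouched.

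The sensitivity analyses do not repair the rule. Protocol 9.7.3 varies the gap and SAP 10.1.3 cuts it to zero, but the listed sensitivity tables (45 to 58) do not repeat the withdrawal outcome (Table 37).

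**Conclusion.** The rule is wrong as written, for one secondary outcome: NOCDURNA patients, Sweden, intensive-care events. Under the Protocol's own gap and intake assumptions, stop-causing events fall outside the window for any supply above 7 days, and at 50% adherence for any supply of 14 days or more. Across the readings and intakes examined, capture ranges from 0% to 47% at S=30 and from 0% to 16% at S=90, so most target events are missed on every reading. Under either gap-based date, the window at one lyophilisate per day contains only days after supply has ended. The size rests on assumed supply lengths and uniform event times; the position of the Protocol window after supply rests only on the documents' own rules.

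**What to change.** State one cessation date for this outcome. Reconcile Protocol 9.2.3.1, 9.3.1 and 9.3.2.2 with both statements in SAP 9.1.1, including the two gap lengths.

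Replace the 14-day look-back in Protocol 9.3.2.2 and 9.7.2.10, and in SAP 2.1.2 and 10.2.9, with a rule anchored on the event:
- Count a serious MACE or VTE that occurs between a NOCDURNA dispensation and the end of that supply (+7 days), when no further NOCDURNA is dispensed within supply plus permissible gap.
- Require the patient to be alive and under observation through that period. Report deaths and censored patients separately; otherwise everyone who dies after the event counts as a withdrawal.
- Report the share of on-treatment events that were followed by a refill.
- Vary the assumed days of use, for example at 0.5 per day.

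Describe the result as events temporally associated with stopping. It is not an upper bound: a patient using fewer than one per day can have a stop-causing event later than supply + 7 days, which this rule misses.

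The cost is revised wording and limited programming on the Swedish dispensing and intensive-care data already planned for linkage. The downside is that some coincidental stops will be counted.

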7. In addition, a subgroup analysis of all patients adhering to the label as assessed by the proxy based on diagnosis and contra-indications (as available) will be conducted.

8.

- 9. Estimate the incidence rate of primary and secondary outcomes of interest between patients treated with NOCDURNA compared to a population of LUTS patients adjusted for confounding factors, by country where data available.
- 10. Estimate the incidence rate of cardiovascular and thromboembolic events of interest resulting in treatment withdrawal of NOCDURNA.

All secondary objectives will be evaluated in the overall population and among subgroups of interest (including elderly, aged ≥65 years).

9 **RESEARCH METHODS**

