9.4.2 Germany

The German Pharmacoepidemiological Research Database (GePaRD) consists of claims information from providers of statutory health insurance (SHI) in Germany (17). GePaRD currently holds data on more than 25 million individuals who have been insured with one of the participating providers since 2004 or later. Per data year, the database includes information on approximately 17% of the general population from all geographical regions of the country. The database was established in 2004 and is managed by the Leibniz Institute for Prevention Research and Epidemiology (BIPS GmbH). The database comprises information on all reimbursable drug dispensations and all reimbursable outpatient (i.e., from general practitioners and specialists) and inpatient diagnoses and services as well as demographics. The ICD-10-GM and ATC coding systems are used for diagnosis and dispensation data, respectively. Additional pharmaceutical information can be obtained through linkage of the central pharmaceutical number in GePaRD to the respective ATC code and additional information (e.g. brand, manufacturer, number of units and strenath of unit). The GePaRD database is regularly used for pharmacoepidemiological research. Information can be accessed upon collaboration and study specific approval with BIPS for projects with public health interest and scientific relevance.

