10.2.8 Secondary objective 7: Comparative analyses

Where possible, for the comparative analyses of primary and secondary outcomes of interest, the same analyses (Poisson regression) as in Section 10.1.2 will be applied but now with treatment group (Nocdurna ®/LUTS) as an additional factor. Patients in the two groups will have their exposure time terminated when patients switch treatment (from Nocdurna to LUTS treatment or from LUTS treatment to Nocdurna). To investigate if the incidence rate ratio (IRR) for the Poisson regression of Nocdurna ® to LUTS depend on confounders, treatment by confounder interaction terms will be investigated to see if and to what extent the IRR depend on the respective confounding factor (age class and gender). A SAS macro have been developed for performing the analysis and is documented in 16.2. The output of the analysis is shown in Table 29. The analysis will show the percent change in the Nocdurna ® group as compared with the LUTS group (using the other variables as covariates), the percent change in the age class 65 to <= 75 year and above or equal 75 years as compared with the <65 year age class, and the percent change in the males as compared with the females. Also the 95% CI and the standard error of the means change are calculated, together with the p-value. The scale value for the model is calculated. The LUTS group is used as reference to ease the interpretation. Observe also that the Poisson regression is the same as the Section 10.1.2, but the output is changed to find the incidence rate ratios (IRR) instead of the incidence rates (IR) themselves. If the model does not converge/modelling assumptions are not met, only unadjusted rate ratios will be presented.

10.2.9 Secondary objective 8: Cardiovascular and thromboembolic events of interest resulting in treatment withdrawal

The analysis of this outcome will be performed analogous to that of incident events of symptomatic hyponatraemia in Section 10.1.2, but only for the Nocdurna ® patients. MACE and VTE events considered to be associated with treatment cessation will be those events for which the event date occurs within 14 days prior to the treatment cessation date. Serious MACE and VTE events will be defined as a primary or secondary diagnosis of MACE or VTE recorded in a hospital intensive care unit. This differs from the normal definition of serious adverse event. This can only be evaluated in Sweden.

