10.3 Data used for meta-analysis

The protocol specifies that a meta-analysis should be included in the final report planned for December 2023. However, it is important to already now to investigate similarities and differences in the databases to be able to suggest the correct analysis to be done and not comparing different data from the three countries. The statistical methods will also by specified in this SAP. The calculations will be made by the Swedish statistician, e.g. no calculations are needed by BIPS or Statistics Denmark as shown in Table 6.

Objective	Denmark	Germany	Sweden	Meta- analysis
Primary objective, rate of low Na by diagnose code	Recorded from hospitals	Recorded from practitioners and specialists and hospitals*)	Recorded from hospitals	Maybe
Sec. Objective 1, descriptive statistics	Data	Data	Data	ОК
Sec. Objective 2, low Na treated at ICU	No data	No Data	Data from a specialized ICU register	Not possible
Sec. Objective 3, low lab. values of Na	Clinical database	No Data	No Data	Not possible
Sec. Objective 4, All-cause mortality	Data	Data (no reason for death)	Data	ОК
Sec. Objective 5a, MACE	Recorded from hospitals	Recorded from practitioners and specialists and hospitals*)	Recorded from hospitals	Maybe
Sec. Objective 5b, VTE	Recorded from hospitals	Recorded from practitioners and specialists and hospitals*)	Recorded from hospitals	Maybe
Sec. Objective 6, CHF	Recorded from hospitals	Recorded from practitioners and specialists and hospitals*)	Recorded from hospitals	Maybe
Sec. Objective 7, Comparing	Repeat primary analysis + sec. 2, 3, 4, 5a, 5b, 6.	Repeat primary analysis + sec. 2, 3, 4, 5a, 5b, 6.	Repeat primary analysis + sec. 2, 3, 4, 5a, 5b, 6.	Look at the other rows

T 11 5 0° 1 1	1.00	1 / /1			• 11 2	, ·
Table 5. Similarities and	differences	between th	he outcome	measures	in the 3	countries

Nocdurna ® vs LUTS Sec. Objective 8, treatment withdrawal	No Data	No Data	Data from drug registry	Not possible
Sec. Objective 9, treatment on label	Repeat primary analysis + sec. 3, 4, 5a, 5b, 6.	Repeat primary analysis + sec. 4, 5a, 5b, 6.	Repeat primary analysis + sec. 2, 4, 5a, 5b, 6.	Primary obj. + secondary 1-6

Abbreviations: ICU = Intensitive Care Unit, MACE = major cardiovascular events, VTE = major venous thromboembolic events, CHF = congestive heart failure. *) German data could be sub-divided and German data are discharge data (in-patient hospital care).

Comment to the table about meta-analysis.

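### The withdrawal objective covers all cardiovascular and thromboembolic events, but the outcome counts only those recorded in Swedish intensive care

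*Protocol*

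**What the plan says.** **Objective.** Protocol section 8 reads "Estimate the incidence rate of cardiovascular and thromboembolic events of interest resulting in treatment withdrawal of NOCDURNA". Neither this wording nor the abstract's outcome list mentions seriousness, intensive care or a single country.

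**Outcome.** In 9.3.2.2, outcome 7 moves to serious events, which are MACE or VTE diagnoses, primary or secondary, "recorded in a hospital intensive care unit. This can be only evaluated in Sweden". Attribution is by timing: "Serious events will be evaluated in 14 days prior to the treatment cessation date". Table 2 lists the item as serious adverse events, Sweden only.

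**Analysis.** Section 9.7.2.10 first treats any MACE or VTE within 14 days before cessation as associated with it, with no ICU condition, and only then adds the ICU definition and the limit to Sweden. The method is that of 9.7.2.1: Poisson regression adjusted for gender and three age classes, with separate models for the first month and for later months.

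**Data.** Dispensings are held in Denmark (9.4.1.2), Sweden (9.4.3.2) and Germany (9.4.2: "The database comprises information on all reimbursable drug dispensations and all reimbursable outpatient", and inpatient, diagnoses). Outcomes 4 and 5 use non-fatal MACE and VTE diagnoses in all three countries. Only ICU information is confined to Sweden.

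**The concern.** The outcome is narrower than the objective it is meant to answer. Treatment cessation is derived from dispensings, which every source holds, and the events are already ascertained in every source for outcomes 4 and 5. Only the ICU condition removes Denmark and Germany. Within Sweden it also sets aside MACE and VTE diagnoses that the National Patient Registry supplies.

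Elsewhere in 9.3.2.2, ICU-recorded MACE and VTE are reported in addition to the overall outcome. Here they replace it. Section 9.9.2 warns of limited data only for ICU hyponatraemia and laboratory hyponatraemia, so a reader of the withdrawal result is not told how much was excluded by definition. At stake is a very small count reported as the rate of withdrawal-related events, from a model that such a count cannot support.

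**Working it through.** **1. The protocol's patient numbers (9.5.3, Table 4).** Lyophilisates / 180 (50% of a 360-day year) x coverage x 4 years:
- Germany: 661,950/180 = 3677.5; x 0.18 = 662; x 4 = 2648 (stated 2650).
- Sweden: 117,250/180 = 651.4; x 4 = 2606 (stated 2610).
- Denmark: 82,260/180 = 457; x 4 = 1828 (stated 1830).

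The figures reproduce. The total is 2650 + 2610 + 1830 = 7090, and Sweden is 2610/7090 = 37%. Adding four annual figures counts a patient treated in several years more than once, so 2610 distinct Swedish patients may be too high.

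**2. Assumptions, none of them in the protocol.** MACE plus VTE rate 10-40 per 1000 person-years (central 20); ICU-recorded share 5-20% (central 10%); treated time 0.25-1.0 years per patient (central 0.5); 50% stop after the event. The 14-day window catches 14/90 to 14/30 of those stops, that is, an event on a random day of a final 30- to 90-day supply, with cessation dated at the end of supply.

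**3. Events that prompted a stop and are captured** = patients x treated years x rate x ICU share x 0.5 x window fraction.
- Protocol definition, central: 2610 x 0.5 x 0.020 x 0.10 = 2.61; x 0.5 x 14/90 = 0.20; x 0.5 x 14/30 = 0.61. At 0.61 the Poisson probability of no event is exp(-0.61) = 0.54.
- Three countries, hospital diagnoses, central: 7090 x 0.5 x 0.020 = 70.9; x 0.5 x 14/90 = 5.5; x 0.5 x 14/30 = 16.5.

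**4. Chance events in the window** = patients x 14/365.25 x rate (x ICU share). Sweden: 2610 x 14/365.25 = 100 person-years. Three countries: 7090 x 14/365.25 = 272 person-years.

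| | Sweden, ICU-recorded | Three countries, hospital diagnoses |
|---|---|---|
| All assumptions low | 0.03 | 1.4 |
| Central | 0.2-0.6 | 5.5-16.5 |
| All assumptions high | 4.9 | 66 |
| Chance events in window | 0.05-0.8 | 2.7-10.9 |

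Of the 27 combinations of low, central and high values for treated time, rate and ICU share, four exceed two captured events for Sweden at the 14/30 fraction, and none does at 14/90.

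**5. Relative yield.** The ratio between the two definitions is (7090/2610) / ICU share = 2.72/0.20 = 14 to 2.72/0.05 = 54. The assumed rate, treated time, stopping probability and window fraction cancel.

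**6. Cessation date.** Section 9.3.1 sets the permissible gap at twice the days supplied. Outcome 7 ties cessation to exceeding that gap, and 9.2.3.1 refers to end of treatment plus 7 days. For a last supply of D days, the gap ends 3D days after dispensing. If that is the cessation date, the window opens at 3D - 14, which is at or after the end of supply (D) whenever D is 7 or more. An event that ended treatment during the supplied days then cannot fall in the window. The window fractions in step 2 apply only if cessation is the end of supply.

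**The case against.** **A declared choice.** Outcome 7 openly defines serious events and states the country limit, and requiring severity can make a timing-based proxy more specific. This stands against any suggestion of concealment. It does not make the measure an estimate of the objective as worded, and severity is already covered by the separate Swedish ICU reporting of MACE and VTE.

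**Section 9.7.2.10 is less restrictive.** True: it can be read as counting all MACE and VTE first and serious ones second. Outcome 7 and Table 2 point to the ICU reading, so the text is inconsistent as well as narrow.

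**More events, not better ones.** A wider definition admits coincidental events, about 3-11 under these assumptions, and if cessation is dated at the end of the gap it would add mainly those. This stands, and it is why the cessation date has to be settled together with the definition.

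**Stronger readings that the documents do not support.** A reader might infer that the count will be close to zero; no rate or ICU share is documented, and the assumed range reaches about 5. A reader might take all on-treatment MACE/VTE (70.9 in the central case) as the gain from dropping the ICU condition; only events inside the 14-day window count. A reader might also conclude that cardiovascular safety goes unmeasured; outcomes 4 and 5 still estimate MACE and VTE in all three countries.

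**Conclusion.** The concern holds as a mismatch between objective and outcome. The objective has no ICU or country condition, the outcome has both, and the country limit follows only from the ICU condition. This rests on the protocol text alone.

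The size rests on the assumptions listed in the working. Under them the protocol definition would capture likely none or a handful of events, too few for the adjusted, time-split Poisson model of 9.7.2.10. Hospital diagnoses in three countries would yield 14 to 54 times as many, depending only on the assumed ICU share and the protocol's patient estimates. Both sets of counts presume that cessation is dated at the end of supply, which the protocol leaves open. The point should be corrected before the outcome is analysed.

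**What to change.** - In 9.3.2.2 outcome 7, Table 2 and 9.7.2.10, count the MACE and VTE diagnoses already defined for outcomes 4 and 5, in Denmark, Germany (discharge diagnoses) and Sweden.
- Keep ICU-recorded events as a separate Swedish sub-analysis.
- State in 9.9.2 that the link between event and withdrawal is temporal only and that some counted events will be coincidental.
- Reconcile 9.2.3.1, 9.3.1 and outcome 7 on whether the cessation date is the end of supply or the end of the permissible gap, so that the 14-day window can include events that ended treatment.

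If the ICU definition is kept, the minimum is to reword the objective to match it and add this outcome to the limitations in 9.9.2.

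Cost: wording changes and one further analysis per country on data already needed for outcomes 4 and 5; no new data source. The drawback is that less severe and some coincidental events enter the outcome, hence the separate ICU row.
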